8.2 Discussion of Trial Design, Including the Choice of Control Groups

As detailed in Section 8.1, this is a prospective, multicenter, randomized, evaluator-blind, controlled trial. The trial will be conducted at approximately five sites to improve data homogenization and to minimize site-associated biases. This multicenter design approach will also increase the representativeness of the trial results. Randomization will eliminate selection bias in treatment assignment.

Since no approved, marketed, directly comparable products are currently available in China for treatment of lower face and submental laxity, an untreated Control Group will be used for the primary effectiveness assessment in this trial. To maximize the number of subjects exposed to acquire adequate safety data, subjects in the Control Group will receive delayed treatment with the Ulthera DeepSEE System at Day 90 upon completion of all effectiveness assessments.

The trial duration of 180 days represents a reasonable timeframe to assess effectiveness as well as delayed-onset and/or long-term AEs. A single treatment protocol using three transducers targeting specific tissue depths at a variable energy level was chosen based on published results. Those studies indicate effectiveness for the majority of subjects and capture of any potential AEs at 90 days following treatment.[2, 8, 9] Following the Treatment Group until Day 180 ensures capture of any late responders to treatment as well as potential delayed-onset or long-term AEs.

Ulthera DeepSEE treatment maps used in this trial (Section 10.5.1.3) represent a safe standard for treatment of the lower face and submentum based on the consensus guidelines.[13] As recommended by the consensus guideline, for the majority of individuals, use of the DS 10-1.5 and DS 7-3.0 transducers are appropriate for treatment of the mid-to-deep reticular layer of the dermis and subdermis, whereas the DS 7-3.0 and DS 7-4.5 transducers are utilized to target the deeper facial planes such as the superficial musculoaponeurotic system and platysma, dependent on individual anatomy and the aesthetic subunit being treated. Pre-treatment visualization of the tissue depths in each subject is used to preclude treatment at the level of large neurovascular structures or bone.

The MFU energy levels are initially set at what are generally considered the highest tolerable levels, and will be titrated as needed for subject comfort, based on the consensus guidelines. It is accepted best practice to provide treatment at multiple energy levels at the discretion of the treating provider, without comprising results by maintaining the proper treatment line density.[13]

9 TRIAL POPULATION AND RESTRICTIONS

9.1 Number of Subjects and Sites

Assuming a screen failure rate of 20%, approximately 250 subjects are planned for screening. Of these, a total of 200 subjects will be randomized at approximately five investigative sites in China. Enrolled subjects will sign and date the ICF before any trial-related procedures are undertaken. At each of the investigative sites, the number of subjects randomized should not exceed 60 to ensure a reasonable distribution of subjects across all investigative sites.

Any subject who does not complete the trial will not be replaced.

Additional information regarding the estimation of sample size is reported in Section 13.1. Further information related to subject randomization is provided in Section 13.2.

9.2 Selection of Subject Population

Assessment for eligibility criteria is based on the subject's medical records, an interview with the candidate subject, and investigator judgment. Selection criteria have been chosen to identify a suitable and representative subject population to investigate the trial objectives and to minimize safety concerns in this population. All investigators will be trained prior to trial start to identify subjects with trial-appropriate lower face and/or submental laxity

[figure not shown]
Following completion of all training activities at each investigative site, approximately five subjects as selected by the investigator for potential enrollment and randomization will be confirmed for trial-appropriate lower face and/or submental laxity during the screening period.

9.2.1 Inclusion Criteria

To be eligible for trial participation, each subject must meet all of the following criteria at screening (Day -14 to -3; Visit 1 [V1]) and Day 1 (V2):

Healthy male or female aged 35 to 65 years at the time of screening.

Has mild to moderate lower face and/or submental laxity that is amenable to improvement with non-invasive intervention and is not severe enough for surgical intervention.

9.2.2 Exclusion Criteria

[figure not shown]
Subjects meeting any of the following criteria at screening (Day -14 to -3; V1) and Day 1 (V2) are not eligible to participate in the trial:

[figure not shown]
Scarring in area(s) to be treated.

Any active implants (e.g., pacemakers or defibrillators) in the area(s) to be treated Any metallic implants in area(s) to be treated.

Any open wounds or lesions , in the area(s) to be treated.

9.2.4 Subject Enrollment and Randomization

Subjects are considered to be enrolled once the ICF is signed and dated. Eligible subjects will be randomized during the screening period (Day -14 to -3). Randomization assignment will not be disclosed to the subjects until Visit 2 (Day 1).

Screen failures are defined in Section 9.2.5.

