9.2.5 Screen Failures

Subjects who provide informed consent but who do not meet eligibility criteria or who withdraw consent prior to being randomized will be defined as screen failures. The investigator will maintain all source documentation for all subjects who are considered screen failures. Minimal information will be collected in the electronic data capture (EDC) system for screen failures, such as date of informed consent, demographics, and reason for screen failure. Individuals who do not meet the criteria for participation in this trial (i.e., screen failure) will not be rescreened.

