9.2.6.2 Subject Withdrawal or Discontinuation

Each subject will be followed to the end of trial (EOT), or until the sponsor decides to terminate the trial, whichever comes first. The only reasons a subject will not be followed

for all scheduled visits include withdrawal of consent, continuous noncompliance with protocol requirements, or loss to follow-up (e.g., moving away from trial site; unresponsive to attempts to contact the subject). Additionally, the investigator can discontinue any subject, at any time, if medically necessary.

A subject has the right to withdraw from the trial at any time at his/her own request without any penalty or loss of benefits to which the subject is otherwise entitled. In cases of withdrawn consent, data collected until the date consent was withdrawn will be analyzed as recorded.

If a subject does not attend a required trial visit, the following actions will be taken:

- The site will make every reasonable attempt to contact the subject and reschedule the
 missed visit as soon as possible. Every effort to regain contact with the subject will be
 made (e.g., phone contact on different dates/times, registered mail). All contact
 attempts will be documented.
- If attempts to contact the subject are not successful, the subject will be considered lost to follow-up and discontinued from the trial.

The reason for the subject's discontinuation should be documented in the electronic case report form (eCRF). The investigator should make every attempt to complete the recommended follow-up assessments specified for the EOT visit described in the Schedule of Events (Section 11.1) while fully respecting the subject's rights. If appropriate, according to local regulations, IEC/IRB and Competent Authorities should be informed.

If a non-serious AE is unresolved at the time of the subject's final trial visit, an effort will be made to follow the subject until the AE is resolved or stabilized, the subject is lost to follow-up, or some other resolution of the event occurs. The investigator should make every attempt to follow all SAEs/unanticipated serious adverse device effects (USADEs) to resolution.

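### Subjects are randomized before the Day 1 eligibility check, and the visible text neither withholds the arm from site staff until that check nor clearly classifies a randomized subject who fails it

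*Protocol*

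**What the plan says.** **Eligibility has two time points.** Protocol 9.2.1 requires that "each subject must meet all of the following criteria at screening (Day -14 to -3; Visit 1 [V1]) and Day 1 (V2". Protocol 9.2.2 mirrors this: "Subjects meeting any of the following criteria at screening (Day -14 to -3; V1) and Day 1 (V2) are not eligible to participate".

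**Randomization comes before the second one.** Protocol 9.2.4 says "Eligible subjects will be randomized during the screening period (Day -14 to -3", and 11.1 and 13.2 repeat the window. Protocol 10.3 reserves randomization for subjects who satisfy every criterion and has the electronic system allocate only if the subject is eligible.

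**Who is kept from the arm.** Protocol 9.2.4 says "Randomization assignment will not be disclosed to the subjects until Visit 2 (Day 1". Protocol 10.4.1, 10.4.2 and SAP 2.4.1 describe treating investigators, the coordinator and other personnel as unblinded. Only the evaluators of the primary endpoint are blinded.

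**Status of a Day 1 failure.** Protocol 9.2.5 defines screen failures as consented subjects who "do not meet eligibility criteria or who withdraw consent prior to being randomized". It adds that "Minimal information will be collected in the electronic data capture (EDC) system for screen failures" and that "Individuals who do not meet the criteria for participation in this trial (i.e., screen failure) will not be rescreened". Protocol 9.2.6.2 gives a closed list of reasons for not following a subject "for all scheduled visits include withdrawal of consent, continuous noncompliance with protocol requirements, or loss to follow-up", and lets the investigator discontinue anyone when medically necessary.

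**Analysis.** As far as shown, the full analysis set (FAS) in Protocol 13.3 and SAP 4 is everyone randomized, with a completed-treatment condition for the Treatment Group only. A sensitivity analysis repeats the primary approach in the randomized set.

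**The concern.** The Day 1 half of the eligibility test cannot be known when the allocation gate in 10.3 is passed, at least three days earlier. A check that falls after allocation is harmless only if whoever applies it does not know the arm, or if failing it changes neither follow-up nor analysis. The visible text secures neither.

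One criterion is a judgement that bears on expected response: whether laxity can improve without invasive treatment and is not severe enough for surgery. If that judgement is revisited on Day 1 with the arm known, subjects could be selected differently in the two arms. Blinded evaluators would not correct this, because it concerns who is assessed rather than how.

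The classification gap adds to this. Two sites could treat the same Day 1 failure in opposite ways, one collecting minimal data as for a screen failure and the other following the subject to Day 180.

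**Working it through.** **1. The plan's own figure.** Protocol 9.1 plans 250 screened for 200 randomized at 20% screen failure: 200 / (1 - 0.20) = 250, reproduced. The visible text gives no expected number of Day 1 failures and does not say whether the 20% includes them.

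**2. A randomized subject who fails on Day 1, read through the sections.**

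| Question | One reading | Other reading |
|---|---|---|
| 9.2.5: does the limit to the time before randomization apply to eligibility failures? | No, it applies to consent withdrawal only. The subject is a screen failure (its last sentence supports this) | Yes. The subject is not a screen failure |
| Data collected | Minimal | Full follow-up, since 9.2.6.2 does not list Day 1 ineligibility, unless discontinued as medically necessary |
| FAS if left untreated | Not stated | Leaves the FAS if in Treatment, stays if in Control |

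**3. Size of the shift.** The documents supply neither of these inputs, so both are assumptions: q, the share of Treatment subjects removed on Day 1, and d, how far their expected response lies below the arm mean p. From p = (1 - q)r + q(p - d), the rate among those who remain is r = p + qd/(1 - q).

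- d = 0: shift 0.
- q = 2%, d = 20 points: 0.02 x 0.20 / 0.98 = 0.41 points. The odds ratio is multiplied by about 1.02 for p of 30-70%.
- q = 5%, d = 20 points: 0.05 x 0.20 / 0.95 = 1.05 points (factor 1.04-1.05).
- Extreme, q = 5%, d = 50 points, p = 50% (no removed subject would have improved): 0.05 x 0.50 / 0.95 = 2.63 points (factor 1.11).

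**4. False success favouring Treatment.** Assume no true effect, 100 randomized per arm, no Control subject removed, and a two-sided 5% pooled z-test in place of the planned logistic model. With shift D = qd/(1 - q), pooled standard error s0 and unpooled standard error s1, the chance is 1 - Phi[(1.96 s0 - D)/s1].

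Example, p = 30%, q = 5%, d = 20: arms of 95 and 100, r = 0.3105, pooled rate 0.3051, s0 = s1 = 0.0660. Then (0.1293 - 0.0105)/0.0660 = 1.80, which gives 3.6%.

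| p | q | d = 0 | d = 10 | d = 20 |
|---|---|---|---|---|
| 20% | 2% | 2.50% | 2.72% | 2.95% |
| 20% | 5% | 2.50% | 3.09% | 3.78% |
| 30% | 2% | 2.50% | 2.69% | 2.89% |
| 30% | 5% | 2.50% | 3.01% | 3.59% |
| 50% | 2% | 2.50% | 2.67% | 2.85% |
| 50% | 5% | 2.50% | 2.96% | 3.49% |

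In the p = 20%, d = 20 cells the removed subjects have 20 - 20 = 0% chance of improving, so those cells are worst cases.

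**5. Same removal in both arms.** With equal q and d the two arms shift by the same amount, the expected difference is zero, and the rate is 2.5% in every row.

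**The case against.** The strongest objection is that the computed inflation comes from another rule. Every figure above 2.5% needs Treatment subjects to leave the analysis while Control subjects stay, and that follows from the completed-treatment condition in the FAS. This stands. Early randomization only adds cases to that asymmetry, and what it contributes by itself is the possibility of an arm-aware decision.

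The judgement route also looks narrow. Investigators are trained on laxity, about the first five subjects per site are confirmed at screening (Protocol 8.1, 9.2), and eligibility must be traceable in source (14.3). A laxity exclusion on Day 1 would usually reverse the investigator's own assessment of 3 to 14 days before. Visible criteria more likely to change in that time, such as open wounds, have no evident link to prognosis, so d would be near 0. This stands too, and it is why the effect is probably small.

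There are safeguards. Section 10.5 requires the criteria for treatment to be met and documented first. The randomized-set analysis follows the primary approach, which the sensitivity list shows to use multiple imputation. That keeps such subjects in, but cannot fully recover outcomes nobody observed.

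Three stronger readings are tempting and are not supported:

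- **Allocation concealment is broken.** The list is computer-generated and the system assigns the arm, so concealment at randomization is intact.
- **Staff do exclude by arm.** Nothing shows this.
- **The plan has no rule on disclosure to staff.** Section 9.2.3, the Schedule of Events and parts of 10.4 and SAP 2.3 are not shown and could contain one.

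None of this removes the conflict in timing or the ambiguity in 9.2.5, which are in the current text.

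**Conclusion.** The point holds as a minor one. The entry criteria must be met on Day 1, yet subjects described as eligible are randomized at least three days earlier. The visible non-disclosure rule covers subjects only, and the status of a randomized Day 1 failure can be read two ways.

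If 2-5% of Treatment subjects were removed and their expected response lay 10 points below the arm mean, the chance of a false result favouring Treatment would be about 2.7-3.1%. At 20 points it would be about 2.9-3.8%. The nominal value is 2.5%. These figures rest on assumed q, d and response rates, a simplified test, and removal from Treatment only. The effect is zero if removal is unrelated to prognosis.

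A reader might infer that early randomization by itself inflates the type I error. The documents do not support that: the one-sided removal comes from the FAS rule, and no figure for Day 1 failures is given.

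**What to change.** **Preferred.** Reconcile Protocol 9.2.1 and 9.2.2 with 9.2.4, 10.3, 11.1, 13.2 and the Schedule of Events, so that the recorded Day 1 eligibility entry precedes allocation in the data capture system. State in 9.2.5 that anyone who fails or withdraws before that point is a screen failure. Baseline assessments stay before Day 1, as SAP 6.4.2 defines them; only the eligibility entry needs to fall on Day 1.

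**If advance randomization is kept for scheduling:**

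- Do not release the arm to site staff until the Day 1 eligibility entry is locked, with matching edits to Protocol 10.4.2 and SAP 2.4.1.
- State in 9.2.5 that a randomized subject who fails on Day 1 is not a screen failure and is followed under 9.2.6.2.
- Apply the same analysis-set rule in both arms (Protocol 13.3, SAP 4).

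**Cost.** Wording changes and small edits to the data capture system and case report form; the system already checks eligibility data before allocating. With the preferred change, treatment slots must be held for everyone attending Day 1, and a few more subjects may need to be screened.

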9.2.5 Screen Failures

Subjects who provide informed consent but who do not meet eligibility criteria or who withdraw consent prior to being randomized will be defined as screen failures. The investigator will maintain all source documentation for all subjects who are considered screen failures. Minimal information will be collected in the electronic data capture (EDC) system for screen failures, such as date of informed consent, demographics, and reason for screen failure. Individuals who do not meet the criteria for participation in this trial (i.e., screen failure) will not be rescreened.

9.2.6 Removal of Subjects from Therapy or Assessment

9.2.6.1 Treatment Discontinuation

If trial treatment is discontinued during administration, the investigator will record the reason for treatment discontinuation in the trial records. If the subject experiences escalating pain or discomfort during treatment with the Ulthera DeepSEE System that is not adequately controlled, the investigator may reduce transducer energy level to improve treatment tolerability (see Section 10.5.1.3). If subject pain or discomfort is not improved by energy level reduction, the investigator may use his/her discretion to suspend treatment to allow for additional pain management measures (see Section 10.5.1.2). Attempts should be made to optimize pain medication so that treatment can be completed.

The investigator may request that a subject discontinuing treatment continue to participate in the trial and complete all remaining visits and assessments for safety follow-up. For subjects who decline to continue trial participation after treatment discontinuation, additional information regarding subject withdrawal is provided in Section 9.2.6.2.

9.2.6.2 Subject Withdrawal or Discontinuation

Each subject will be followed to the end of trial (EOT), or until the sponsor decides to terminate the trial, whichever comes first. The only reasons a subject will not be followed

for all scheduled visits include withdrawal of consent, continuous noncompliance with protocol requirements, or loss to follow-up (e.g., moving away from trial site; unresponsive to attempts to contact the subject). Additionally, the investigator can discontinue any subject, at any time, if medically necessary.

A subject has the right to withdraw from the trial at any time at his/her own request without any penalty or loss of benefits to which the subject is otherwise entitled. In cases of withdrawn consent, data collected until the date consent was withdrawn will be analyzed as recorded.

If a subject does not attend a required trial visit, the following actions will be taken:

- The site will make every reasonable attempt to contact the subject and reschedule the
 missed visit as soon as possible. Every effort to regain contact with the subject will be
 made (e.g., phone contact on different dates/times, registered mail). All contact
 attempts will be documented.
- If attempts to contact the subject are not successful, the subject will be considered lost to follow-up and discontinued from the trial.

The reason for the subject's discontinuation should be documented in the electronic case report form (eCRF). The investigator should make every attempt to complete the recommended follow-up assessments specified for the EOT visit described in the Schedule of Events (Section 11.1) while fully respecting the subject's rights. If appropriate, according to local regulations, IEC/IRB and Competent Authorities should be informed.

If a non-serious AE is unresolved at the time of the subject's final trial visit, an effort will be made to follow the subject until the AE is resolved or stabilized, the subject is lost to follow-up, or some other resolution of the event occurs. The investigator should make every attempt to follow all SAEs/unanticipated serious adverse device effects (USADEs) to resolution.

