10.4 Blinding Procedures

10.4.1 Blinding

In this prospective trial, the treating investigators and subjects will not be blinded to trial treatment. For the primary effectiveness endpoint only (proportion of subjects with improvement in lower face and submental skin laxity; see Section 7.2.1.1), the blinded evaluators will be blinded to trial group assignment.

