12.5 Reporting of Pregnancy

Any pregnancy that starts during the clinical trial must be reported by the investigator to the sponsor and CRO immediately. Pregnancies and pregnancy follow-up should be reported on a Pregnancy Form. Pregnancy follow-up should describe the outcome of the pregnancy, including any voluntary or spontaneous discontinuation; details of the birth; the presence or absence of any congenital abnormalities, birth defects, maternal or newborn complications, and their relation to the IMD. In addition, each pregnancy has to be reported on the AE eCRF page (i.e., as a non-serious AE due to device exposure before or during

pregnancy). Pregnancy Forms (including any follow-up forms) should be submitted to the contacts referenced in Section 12.2.2.

If a subject becomes pregnant during the trial, the subject must not receive treatment (i.e., delayed treatment for subjects in the Control Group); however, the subject will remain in the trial.

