13.3 Populations for Analysis

The following analysis sets will be defined:

- The randomized set is defined as all subjects randomized into the trial;
- The Safety Evaluation Set (SES) is defined as all subjects treated;

- The Full analysis Set (FAS) is defined as all subjects randomized

 Subjects randomized to the Treatment Group must also finish the treatment;
- The Per Protocol Set (PPS) is the subset of subjects in the FAS who have no major
 protocol deviations potentially biasing the statistical analysis of the primary endpoint.
 Final determination of what constitutes major or minor protocol deviations in this sense
 will be made prior to database close.

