13.4.1 Effectiveness Analyses

If not otherwise specified, effectiveness analyses will be based on observed cases in the FAS. For the FAS, all subjects will be analyzed as randomized.

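### Protocol 9.2.6.2 lets scheduled follow-up stop for undefined continuous noncompliance, so Day 90 outcomes and new late non-serious AEs can be lost although they could have been collected

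*Protocol*

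**What the plan says.** Protocol 9.2.6.2 starts from a clear default: "Each subject will be followed to the end of trial (EOT), or until the sponsor decides to terminate the trial, whichever comes first". It then gives what is presented as an exhaustive list of reasons for not following a subject through all scheduled visits. These "include withdrawal of consent, continuous noncompliance with protocol requirements, or loss to follow-up". The next sentence adds a further ground: "Additionally, the investigator can discontinue any subject, at any time, if medically necessary".

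The same section limits the damage. After discontinuation the EOT assessments are to be attempted, non-serious AEs still open at the final visit are to be followed, and every attempt is to be made to follow SAEs and USADEs to resolution. Section 11.1 repeats the EOT visit.

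Other relevant text:
- 10.4.1: "the treating investigators and subjects will not be blinded to trial treatment". Only the evaluators of the primary endpoint are blinded.
- 10.5.2: each subject has a single treatment, on Day 1 or, for Controls, at Day 90.
- 9.1: subjects who do not complete are not replaced.
- 13.3: the PPS "is the subset of subjects in the FAS who have no major" protocol deviations that could bias the primary analysis.
- 13.4.1: "For the FAS, all subjects will be analyzed as randomized", with observed cases as the default for effectiveness analyses.
- 12.5: a subject who becomes pregnant is not treated; "however, the subject will remain in the trial".

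**The concern.** Withdrawn consent and lost contact make further data unobtainable. Noncompliance does not: a subject who has broken a protocol requirement can still be photographed, rated and asked about adverse events. Stopping that subject's visits therefore gives up data that could be had. It also brings a per-protocol kind of selection into the FAS and the randomized-set analysis, although the PPS exists for that purpose.

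Because treatment is one session, ending a Treatment Group subject's participation after Day 1 withdraws no further device exposure and only ends observation. For a Control before Day 90, the only trial treatment left to withhold is the delayed session.

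The loss could differ by arm. Allocation is known to investigators and subjects, only the Treatment Group can have device effects before Day 90, and Controls wait untreated. At stake are the single confirmatory comparison at Day 90, the displacement test, and the capture of delayed AEs that Protocol 8.2 gives as a reason for following the Treatment Group to Day 180.

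**Working it through.** **The plan's own figures.** None bears on this point. No discontinuation rate is visible, and the text of Protocol 13.1, Protocol 13.5.1 and SAP section 3 is not shown. The one related count that can be checked is screening: 200 / (1 − 0.20) = 250, which agrees with Protocol 9.1. It covers screen failures, not losses after randomization.

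**Step 1: what is lost when visits stop.**
- *Before the Day 90 window (±7 days, Protocol 11.1).* The EOT visit gives an early assessment but no Day 90 outcome. The sensitivity-analysis wording in 13.4.1.1 shows that the primary analysis uses multiple imputation. That fills the gap under a model but does not recover the value. The randomized-set analysis has the same gap. On the visible text the displacement test uses observed cases, so the subject drops out.
- *After Day 90.* The primary outcome is already in hand. Protocol 12.1.1 ends AE observation at the last trial visit, so new non-serious events after it are not collected. Section 11.2.2.1 still requires device-related SAEs to be reported, though generally not in the clinical database.

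**Step 2: size under assumed rates.** Inputs: 100 per arm (200 randomized 1:1, SAP 2.1); improvement of 60% vs 20% (assumed). Crude observed-case odds ratio = (T improved / T not improved) / (C improved / C not improved).

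| Removed before Day 90 | Calculation | Odds ratio |
|---|---|---|
| Nobody | (60/40)/(20/80) | 6.0 |
| 5 Treatment, in proportion (3 improvers, 2 not) | (57/38)/(20/80) | 6.0 |
| 5 Treatment non-improvers | (60/35)/(20/80) | 6.9 |
| 10 Treatment non-improvers | (60/30)/(20/80) | 8.0 |
| 5 improved Controls | (60/40)/(15/80) | 8.0 |
| 5 Treatment improvers | (55/40)/(20/80) | 5.5 |

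With 5 non-improvers gone, the Treatment proportion reads 60/95 = 63.2% instead of 60%. The second and last rows show that the shift depends on who is removed and can go either way.

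**Step 3: error rate with no true effect.** Let both arms have true rate p and remove d Treatment non-improvers. Then
- n₁ = 100 − d, n₂ = 100, p_T = 100p/(100 − d);
- p̄ = (n₁p_T + n₂p)/(n₁ + n₂);
- SE₀ = √[p̄(1 − p̄)(1/n₁ + 1/n₂)] and SE₁ = √[p_T(1 − p_T)/n₁ + p(1 − p)/n₂];
- P(significant in favour of Treatment) ≈ Φ[(p_T − p − 1.96·SE₀)/SE₁].

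Example with p = 0.3 and d = 5: p_T = 0.3158, p̄ = 60/195 = 0.3077, SE₀ = SE₁ = 0.0661. The argument is (0.0158 − 0.1296)/0.0661 = −1.72, which gives 0.043.

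| d | p = 0.2 | p = 0.3 | p = 0.5 |
|---|---|---|---|
| 0 | 0.025 | 0.025 | 0.025 |
| 2 | 0.030 | 0.031 | 0.035 |
| 5 | 0.038 | 0.043 | 0.056 |
| 10 | 0.057 | 0.071 | 0.116 |

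Both calculations describe observed cases. The effect under multiple imputation depends on a model that is not visible.

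**Step 4: the medical-necessity sentence beside related text.**
- 9.2.6.2: the investigator may discontinue any subject.
- 5.2: after an AE or poor tolerability, the investigator judges whether continuing is in the subject's best interest.
- 6.3: a subject whose treatment is stopped as intolerable is followed for AEs for the whole trial.
- 9.2.6.1: the investigator may request that a subject who discontinues treatment stay on for safety follow-up.
- 12.5: a pregnant subject is not treated but stays in the trial.

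These treat stopping treatment and staying in the trial differently, and the sentence in 9.2.6.2 adds a ground after a list presented as complete.

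**The case against.** The strongest reply is that the rule has little room to act before the primary endpoint. Under Protocol 8.1, Controls have no scheduled contact between Day 1 and Day 90. The Treatment Group has safety calls at 3 and 14 days, with weekly calls for ongoing nerve effects under SAP 2.1. There is not much schedule to fail against. This stands, and it suggests few removals before Day 90. It does not settle the matter, because protocol requirements are wider than visits and the text of 9.2.3 on restrictions during the trial is not shown.

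Second, the arithmetic assumes fully selective removal from one arm, yet the primary outcome is first rated at Day 90 by blinded evaluators. Anyone removing a subject earlier does not have that rating. This also stands: the figures mark an extreme, not an expectation.

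Third, the plan has multiple imputation plus observed-case, PPS and randomized-set sensitivity analyses, and the SAP abbreviations include both MAR and MNAR, so a not-at-random analysis may be in text not shown. That softens the concern for the primary endpoint. It does not replace unobserved data.

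Three stronger readings are tempting but unsupported:
- *All follow-up ends.* It does not: 9.2.6.2 and 11.1 call for EOT assessments, and 9.2.6.2 continues follow-up of open AEs and SAEs.
- *The unblinded investigator decides who is noncompliant.* Section 9.2.6.2 gives the investigator only the medical decision and names nobody for noncompliance.
- *Data are in fact lost selectively.* The documents give neither a rate nor a direction.

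**Conclusion.** The concern holds in a limited form. Section 9.2.6.2 contains a stated rule that stops scheduled visits for a reason that does not itself prevent data collection, with no definition and no named decision-maker. Day 90 outcomes and new late non-serious AEs can be lost through it, possibly unequally by arm.

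The size is unknown. It is zero if nobody is removed, and close to zero for the odds ratio if removal is unrelated to outcome. With an assumed 60% vs 20% and 100 per arm, 5 fully selective removals from the Treatment Group move the observed-case odds ratio from 6.0 to 6.9. That would not change the conclusion at so large an assumed effect. With no true effect, the same 5 removals raise the one-directional error from 0.025 to between 0.038 and 0.056 for true rates of 0.2 to 0.5.

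A reader might infer that the confirmatory result is compromised or that the medical-necessity sentence should go. The documents support neither. That sentence leaves a clinical decision with the investigator; the finding there is only that it must be reconciled with 5.2, 6.3, 9.2.6.1 and 12.5.

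**What to change.** 1. In Protocol 9.2.6.2, delete continuous noncompliance as a reason to stop scheduled visits. Record it as a protocol deviation and handle it through the PPS.
2. State that subjects discontinued for any reason other than withdrawn consent or lost contact are asked to attend the Day 90 and Day 180 assessments where possible.
3. Report discontinuation reasons by arm, with matching eCRF categories.
4. Leave the medical decision with the investigator, but reconcile the medical-necessity sentence with the list it follows and with Protocol 5.2, 6.3, 9.2.6.1 and 12.5, so that stopping treatment and leaving the trial are described consistently. No clinical rule is proposed here.

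The cost is one reworded paragraph, a small eCRF change and one table, plus consistency edits in the four related sections. Sites would keep scheduling visits for less cooperative subjects, and keeping those subjects in the FAS may slightly dilute the observed effect.
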